#### 3 STATISTICAL METHODOLOGY

#### 3.1 General Considerations

#### 3.1.1 Analysis Day

Analysis day will be calculated from the date of first dose of study drug. The day of the first dose of study drug will be Day 1, and the day immediately before Day 1 will be Day -1. There will be no Day 0.

#### 3.1.2 Analysis Visits

Nominal visits (i.e., study visits captured on the CRF) will be used for all efficacy and safety analyses.

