1.2. Schema

1.3. Schedule of Activities (SoA)

Study Period	Screening period	Baseline		terim Vi Veeks 2 -		EOT / ET Week 12	Telephone follow-up Week 14	Notes
Day	-14 to -0	1	14 ±3	28 ±3	56 ±3	84 ±3	98 ±3	In the event of early termination (ET) participants should complete the End of Treatment (EoT) assessments
Visit	1	2	3*	4*	5*	6*	7	
Informed consent	X							
Eligibility criteria	X	X						
Randomization		X						
Demographics	X							
Medical history/diagnosis	X							
Prior and concomitant medications	X	Х	Х	X	х	X	Х	Details of excluded and permitted concomitant treatments are presented in Section 6.5.
Vital signs	X	X	X	X	X	X		
12-lead ECG	X					X		
Physical & neurological examination	Х					X		
UMSARS		X		X	X	X		
MSA-QoL		X		X	X	X		
MoCA	X					X		
UDRS		X		х	Х	Х		To be evaluated at approximately the same time of day as at the baseline visit, and this should be at least 1 hour after the patient has taken their daily dose of safinamide and is in the optimal "ON" state, where possible.
Goniometric assessment		X		Х	X	Х		

Study Period	Screening period	Baseline	Interim Visits Weeks 2 - 8		EOT / ET Week 12	Telephone follow-up Week 14	Notes	
Day	-14 to -0	1	14 ±3	28 ±3	56 ±3	84 ±3	98 ±3	In the event of early termination (ET) participants should complete the End of Treatment (EoT) assessments
Visit	1	2	3*	4*	5*	6*	7	
Haematology/Clini cal chemistry	X					X		
Pregnancy test (urine)		X				X		Only for WOCBP.
Adverse events		X	X	X	X	X	X	
Dispense randomized medication		Х	X	Х	X			The first dose of study medication will be administered at the study centre.
Drug accountability			X	X	X	X		

*= COVID-19 outbreak: in order to ensure the continuity of the study, limiting the subjects' exposure to infection and overcoming travel restriction imposed by governments, sites have been allowed to perform these visits using phone call and/or video – consultation.

Everything has been documented in the source data as per guidance distributed to the affected sites.

2. Introduction

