In case of EOT, the visit should be performed in the first day available.

Physical examination including body weight.

- Neurological examination.
- Vital signs (pulse rate, systolic and diastolic blood pressure measured after at least 5 minutes in the supine position).
- 12-lead ECG in the supine position.
- Completion of scales by rater/participant:
 - UMSARS
 - MSA-OoL
 - MoCA
 - UDRS
- Blood sampling for clinical laboratory assessments (hematology and clinical chemistry).
- Urine sampling for urine (dipstick) pregnancy test for women (only for WOCBP).
- Record concomitant medications and therapies.
- Goniometric assessment for "lateral" and "anterior" displacement
- Record AEs.
- Perform drug accountability.

The maximum amount of blood collected from each participant over the duration of the study, including any extra assessments that may be required, will not exceed 10 mL.

Repeat or unscheduled samples may be taken for safety reasons or for technical issues with the samples.

COVID-19 outbreak: in order to ensure the continuity of the study, limiting the subjects' exposure to infection and overcoming travel restriction imposed by governments, sites have been allowed:

- to perform these visits using phone call and/or video consultation
- to manage study medication return at site through a care-giver/family member
- to take Vital Sign using patient's instruments

Everything has been documented in the source data as per guidance distributed to the affected sites.

Visit 7: Telephone Follow-up

After 2 weeks from the End of Treatment, a telephone follow-up with patient should be performed, questioning about:

- Concomitant medications and therapies
- AEs

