8.1.4. Clinical Safety Laboratory Assessments

- See Appendix 2 for the list of clinical laboratory tests to be performed and to the SoA for the timing and frequency.
- The investigator must review the laboratory report, document this review, and record any clinically relevant changes occurring during the study in the AE section of the CRF. The laboratory reports must be filed with the source documents. Clinically significant abnormal laboratory findings are those which are not associated with the underlying disease, unless judged by the investigator to be more severe than expected for the participant's condition.
- All laboratory tests with values considered clinically significantly abnormal during participation in the study or within two (2) weeks after the last dose of study intervention should be repeated until the values return to normal or baseline or are no longer considered clinically significant by the investigator or medical monitor.
 - If such values do not return to normal/baseline within a period of time judged reasonable by the investigator, the etiology should be identified, and the sponsor notified.
 - o All protocol-required laboratory assessments, as defined in Appendix 2, must be conducted in accordance with the laboratory manual and the SoA.

 If laboratory values from non-protocol specified laboratory assessments performed at the institution's local laboratory require a change in participant management or are considered clinically significant by the investigator (e.g., SAE or AE or dose modification), then the results must be recorded in the CRF.

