# 2.3.2 Safety Endpoints

Safety endpoints include the following parameters:

- The nature, frequency, severity, relationship (to study drug), actions taken, and outcome of TEAEs and SAEs.
  - Adverse events will be coded using Medical Dictionary for Regulatory Activities (MedDRA) Version 23.0. The severity of AEs will be assessed using "mild", "moderate" and "severe". The degree of "relatedness" of the AE to the study treatment will be described using "related to study drug" and "not related to study drug".
  - Treatment-emergent adverse events (TEAEs) are defined as those AEs that have a start date on or after the first administration of study drug. AEs with unknown/unreported onset date will also be counted as TEAE.
- Physical and neurological examination findings.
  - Physical and neurological examinations will be performed at Screening and Week 12. Results will be recorded as "abnormal", "normal" and "not assessed".
- Vital sign (heart rate, systolic and diastolic blood pressure) values.
  - o Vital signs will be assessed at Screening, Day 1, 14, 28, 56, and Day 84/Week 12.
- 12-lead Electrocardiogram (ECG) parameter measures.
  - o 12-lead ECG will be performed at Screening and Week 12.
- Clinical chemistry and hematology values.
  - Clinical chemistry and haematology evaluations will be performed at Screening and Week 12.
- Number of withdrawals (and reason if given).
  - O Subject withdrawals from the study will be recorded on the End of Study CRF with reasons provided.

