### 3.5.2 Clinical Laboratory Tests

Values and changes from baseline will be summarized using descriptive statistics for each treatment group by visit for protocol-required laboratory tests in Appendix A. All lab results will be listed.

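### The SAP has no rule for unscheduled or repeat safety results and no worst-value or shift summary, although Visit 6 is the only scheduled post-dose laboratory and ECG assessment

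*SAP*

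**What the plan says.** **Visit rule.** SAP 3.1.2 (version 2.0): "Nominal visits (i.e., study visits captured on the CRF) will be used for all efficacy and safety analyses". The SAP has no sentence on unscheduled or repeat results.

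**Outputs.** For laboratory tests, SAP 3.5.2 says "Values and changes from baseline will be summarized using descriptive statistics for each treatment group by visit", with every result also listed. SAP 3.5.3 lists vital signs and summarises them by arm and visit. SAP 3.5.4 counts the overall ECG interpretation by arm, without saying at which visit, and lists the findings.

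**Timing.** SAP 2.3.2: "Clinical chemistry and haematology evaluations will be performed at Screening and Week 12"; "12-lead ECG will be performed at Screening and Week 12"; "Vital signs will be assessed at Screening, Day 1, 14, 28, 56, and Day 84/Week 12". The Protocol 1.3 schedule adds: "In the event of early termination (ET) participants should complete the End of Treatment (EoT) assessments".

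**Results outside the schedule.** Protocol Section 8, under Visit 6: "Repeat or unscheduled samples may be taken for safety reasons or for technical issues with the samples". Protocol 8.1.4 adds that clinically significant abnormal laboratory tests, during the study or within two weeks of the last dose, "should be repeated until the values return to normal or baseline or are no longer considered clinically significant".

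**Abnormal results.** The safety endpoints in Protocol Section 3 include the occurrence of abnormalities for vital signs, ECG and laboratory values, and laboratory shifts from baseline. Protocol 9.4.1.5 planned low/normal/high shift tables by arm. SAP Section 5 removes shift tables because abnormal findings are expected to be captured as adverse events, and SAP 3.5 says that any abnormal result will be reported as one. Protocol Appendix 3 is narrower: an abnormal result is an adverse event only when the investigator judges it clinically significant. Findings tied to the underlying disease are left out unless more severe than expected.

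**The concern.** Safety is the primary objective, and the laboratory, ECG and vital-sign endpoints belong to it. Many of the extra results that the protocol provides for will come from participants in whom something needed checking. If the only by-arm laboratory value table is tied to Screening and Week 12, an abnormality found at an unscheduled draw in Week 5 and gone by Week 12 contributes only a normal Week 12 value to it. If the Week 12 sample is itself repeated, the SAP does not say whether the first result or the repeat represents the visit. Required repeats stop once a value has settled, so using the last one would usually put the milder value in the table. That choice should not be left open until after unblinding.

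The removal of the shift tables adds to this. It relies on every abnormal finding becoming an adverse event, which the protocol does not require. Without shift tables or a worst-value summary, the SAP counts abnormal laboratory or vital-sign results by arm only through adverse events.

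**Working it through.** The plan states no figure to reproduce. The check is a count of scheduled looks and a trace of where each kind of result ends up.

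**1. Scheduled post-dose looks** (Protocol 1.3, SAP 2.3.2)
- Laboratory: Day 84 only, so 1.
- ECG: Day 84 only, so 1.
- Vital signs: Days 14, 28, 56 and 84, so 4.

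For laboratory tests and ECG, the interval from Day 1 to the first scheduled post-dose look is 84 − 1 = 83 days (visit window ±3 days). It is shorter only for a participant who terminates early and has the Visit 6 assessments then.

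**2. What one look at Day 84 can see (illustration)**

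The documents give neither the duration nor the timing of laboratory abnormalities. Assume one that lasts *w* days, with timing uniform over 84 days. The share present at Day 84 is *w*/84:
- *w* = 7: 7/84 = 8%
- *w* = 14: 14/84 = 17%
- *w* = 28: 28/84 = 33%

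Under this assumption, most short-lived abnormalities would be seen only in unscheduled samples.

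**3. Where each result goes** (usual reading of nominal visits; adverse-event rule from Protocol Appendix 3)

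| Result | By-visit table by arm | Adverse-event table by arm | Listing |
|---|---|---|---|
| Visit 6 laboratory value, out of range, not judged clinically significant | Yes, as one value in the mean and range; not counted as abnormal | No | Yes |
| Unscheduled laboratory value, judged clinically significant | No | Yes, unless attributed to the underlying disease | Yes |
| Unscheduled laboratory value, out of range, not judged clinically significant | No | No | Yes |
| Repeat of a Visit 6 laboratory test | No rule on which result counts | Follows the judgement on the abnormal result | Yes |
| Scheduled abnormal vital sign, not judged clinically significant | Yes, as one value; not counted as abnormal | No | Yes |
| ECG finding, any visit | No value table; interpretation counts do not say which ECGs enter | If judged clinically significant | Yes |

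The third row has no by-arm table at all. In the first and fifth rows the value is tabulated, but only a listing shows that it was abnormal.

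**4. Does the adverse-event route close the gap?**

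Treatment-emergent events are defined by start date (SAP 2.3.2), so the visit rule does not remove them. But SAP 3.5 and Section 5 assume that every abnormal finding becomes an adverse event, while Protocol Appendix 3 admits only those judged clinically significant. The difference between the two is what reaches listings alone.

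**5. Weight of one participant**

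With 26 and 14 evaluable participants (SAP 2.2.3), one participant is 1/26 = 3.8% or 1/14 = 7.1% of an arm. With 48 randomised 2:1, that is 1/32 = 3.1% or 1/16 = 6.3%. Choosing a first or a repeat value for one person can therefore visibly move a mean or a maximum.

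**The case against.** - **No stated exclusion.** SAP 3.1.2 never mentions unscheduled results. Its gloss could cover an unscheduled visit recorded on the CRF, and the separate programming specifications (SAP Section 6) are not available here. This stands: the defect is a missing rule, and the exclusion is inferred from what nominal visits usually means.
- **Nothing is lost.** All laboratory results, vital signs and ECG findings are listed, for about 48 participants. Results judged clinically significant normally reach the by-arm adverse-event tables, and Protocol Appendix 2 makes possible Hy's Law cases serious adverse events. This stands too. What remains in listings alone is mainly results not judged clinically significant.
- **ECG and vital signs differ from laboratory tests.** The protocol's unscheduled and repeat provisions concern laboratory samples, and technical reasons are allowed as well as safety reasons. Vital signs have four scheduled post-baseline points. ECG has no value table for any visit, so the visit rule is not the cause there.
- **Pre-dose repeats can enter.** A repeat screening laboratory test (Protocol 5.4) can become the baseline under SAP 3.1.3. The gap concerns post-baseline values.
- **A worst-value table has its own weakness.** It depends on how often each participant is tested, and descriptive safety analysis in a pilot is legitimate. Both are fair. Neither explains how an endpoint on occurrence of abnormalities is to be reported by arm.

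A reader might infer that the plan discards the worst values and so biases the safety comparison towards no effect. The documents do not support that. A Week 12 table describes Week 12, the number and direction of unscheduled results are unknown, and clinically significant ones have another route into by-arm tables. The bias is plausible but not shown.

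**Conclusion.** The point holds as a gap in the SAP. There is no rule for unscheduled or repeat safety results, no rule for which result represents a repeated visit, and no worst-value or shift summary. Laboratory tests and ECG have one scheduled post-dose look. The reason given for dropping shift tables conflicts with the protocol's definition of an adverse event. As a result, the endpoint on occurrence of abnormalities has no by-arm table for laboratory tests and vital signs beyond adverse events. For ECG the gap is narrower: the interpretation table does not say which ECGs count.

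The conclusion assumes the usual meaning of nominal visits and that sites apply the protocol's adverse-event rule. If sites report every abnormal result as an adverse event, as SAP 3.5 says, much of the gap closes, but the rule for repeats is still missing. The size cannot be estimated, because the documents give no count of unscheduled samples. The single laboratory and ECG look is a feature of the schedule, and a change to the analysis does not remove it. The point is worth settling before unblinding.

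**What to change.** 1. Limit SAP 3.1.2 to by-visit summaries.
2. In SAP 3.5.2, add by arm the worst post-baseline laboratory value or category per participant (low/normal/high against the baseline category), using scheduled, unscheduled and repeat results in the database.
3. In SAP 3.5.3, add the highest and lowest post-baseline value of each vital sign per participant, by arm.
4. In SAP 3.5.4, state which ECGs count, and use the worst post-baseline interpretation per participant.
5. State before unblinding that the first valid result, not the repeat, represents a nominal visit. A repeat stands in only when the first sample was technically invalid.
6. Reconcile SAP 3.5 and Section 5 with Protocol Appendix 3 on when an abnormal result becomes an adverse event.
7. Beside each worst-value table, show the number of post-baseline assessments per arm, so that unequal testing is visible.

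The cost is SAP wording and a few extra tables, with no new assessments. Coverage is limited to what was entered: Protocol 8.1.4 requires non-protocol local laboratory results in the CRF only if they are clinically significant or change the participant's management.

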#### 3.1.3 Definition of Baseline

Baseline measurements refer to data collected at Day 1. If a value at Day 1 is not available, the last measurement prior to the first dose of study medication will be used as the baseline value.

#### 3.1.4 Summary Statistics

Categorical data will be summarized with counts and percentages of subjects. Continuous data will generally be summarized with descriptive statistics including n (number of non-missing values), mean, median, standard deviation, minimum, and maximum.

#### 3.1.5 Hypothesis Testing

Efficacy endpoints will be tested with hypothesis of the form:

$$H_0$$
:  $\mu_{test} = \mu_{placebo}$ 

$$H_1$$
:  $\mu_{test} \neq \mu_{placebo}$ 

where  $\mu$  is the mean value of any specified endpoint in the population.

# 3.2 Analysis Populations

#### 3.2.1 Screened Population

The Screened Population will include all participants who sign the informed consent form (ICF). This population will be listed but not used for statistical analyses.

#### 3.2.2 Intent-to-Treat (ITT) Population

The ITT Population will include all randomized participants. This population will be used for all efficacy variables.

#### 3.2.3 Safety Population

The Safety Population will include all randomized participants who take at least one dose of study medication. This population will be used to summarize all safety data; participants will be analyzed according to the medication they actually received.

#### 3.2.4 Per-Protocol (PP) Population

The PP Population will include all randomized participants who do not have any entry criteria violations or protocol deviations that could significantly impact the assessment or interpretation of efficacy data. Participant data will be reviewed by the clinical team to identify exclusions from the PP Population. The list of participants to be excluded from the PP Population will be finalized prior to database unblinding. This population will be used for the analysis of the leading efficacy variable UMSARS if the number of subjects in the PP Population is less than 90% of that in the ITT Population.

# 3.3 Subject Data and Study Conduct

#### 3.3.1 Subject Disposition

Subject disposition will be provided for all screened subjects. The number and percentage of subjects in the following disposition categories will be presented by treatment and in total:

- Subjects who were screened (signed informed consent);
- Subjects who were screen failures;
- Subjects who were randomized;

- Subjects who completed Week 12, and the whole study (i.e., Week 14 follow-up);
- Subjects who terminated early

For subjects who failed screening and who did not complete the study, a summary will be provided for the reasons. Primary reason for screen failure or early termination due to Covid-19 will also be provided if available.

#### 3.3.2 Protocol Deviations

Protocol deviations (PDs) will be defined in the Medpace Protocol Deviation Plan and captured in the Study Management System. The number and percentage of subjects with CSR-reportable PDs will be summarized for each deviation category and overall based on the ITT Population. PDs related to COVID-19 will be categorized and summarized separately.

CSR-reportable PDs and COVID-19 related non-reportable PDs will be listed.

#### 3.3.3 Analysis Populations

Counts and percentages of subjects in each analysis population will be summarized by treatment and in total based on all screened subjects.

#### 3.3.4 Demographic and Baseline Characteristics

The following demographic and baseline characteristics will be summarized by treatment and in total for all subjects in the ITT Population:

- Age (years)
- Sex
- Childbearing potential
- Height (cm)
- Weight (kg)
- Body mass index (BMI) (kg/m²)

Continuous variables (age, height, weight, BMI) will be summarized with descriptive statistics (n, mean, standard deviation, median, minimum, and maximum). Categorical variables (sex, race, ethnicity, childbearing potential) will be summarized with counts and percentages of subjects.

#### 3.3.5 Medical History

General medical history and diagnosis of MSA for each subject will be provided in data listings for the ITT Population.

#### 3.3.6 Prior and Concomitant Medications / Medical Procedures

Prior and concomitant medications will be coded to anatomical therapeutic chemical (ATC) class and preferred term using the WHODrug Dictionary Global B3, Sept 2019. For summary purposes, medications will be considered prior medications if they stopped prior to the first dose of study drug and concomitant medications if they were taken at any time after the first dose of study drug (i.e. started prior to the first dose of study drug and were ongoing or started after the first dose of study drug).

If a medication has incomplete start or stop dates, dates will be imputed to determine whether a medication should be considered prior or concomitant. If a medication start date is incomplete, the first day of the month will be imputed for missing day and January will be imputed for missing month. If a medication stop date is incomplete, the last day of the month will be imputed for missing day and December will be imputed for missing month. Incomplete start and stop dates will be listed as collected without imputation.

Counts and percentages of subjects taking prior and concomitant medications by ATC class and preferred term will be summarized by treatment and in total based on the ITT Population.

Prior and concomitant medical procedures and non-drug therapies will be listed.

#### 3.3.7 Study Drug Exposure and Compliance

Days of exposure to study drug will be calculated as date of last dose of study drug – date of first dose of study drug + 1. Note that the exposure calculation is intended to describe the length of time a subject was exposed to study drug and therefore does not take study drug interruptions into account. Days of exposure to study drug will be summarized by treatment with descriptive statistics and with counts and percentages of subjects with exposure in the following categories:

- <2 weeks (<14 days)
- 2 <8 weeks (14 55 days)
- 8 < 12 weeks (56 83 days)
- $\geq$ 12 weeks ( $\geq$ 84 days)

Percent compliance to the study drug regimen will be calculated as

100 x (# of tablets dispensed - # of tables returned) / # of tablets expected to be taken.

If study drug is not returned, the number of tablets returned and lost will be considered 0 for the compliance calculation. The number of tablets expected will be calculated as

- Date of last visit Date of randomization + 1, if subjects early terminated prior to Week 2 / Visit 3:
- (Date of last visit Date of Visit 3 + 1) \*2 + (Date of Visit 3 Date of randomization), if subjects early terminated prior to Week 12 / Visit 6;
- (Date of Visit 6 Date of Visit 3 + 1) \*2 + (Date of Visit 3 Date of randomization), if subjects completed the end of treatment visit (i.e., Visit 6);
- Any drug interruptions or temporary discontinuation will be taken into account.

Percent compliance to the study drug regimen will be summarized by treatment with descriptive statistics and with counts and percentages of subjects with compliance in the following categories:

- <80%
- 80-120%
- · >120%

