6.1. Study Intervention(s) Administered

Study Intervention Name:	Active Safinamide methanesulfonate Placebo					
Dosage formulation:	Orange to copper, round, biconcave film-coated tablets					
Unit dose strength(s)/Dosage level(s):	100 mg (free base)	Only excipients: microcrystalline cellulose, crospovidone, colloidal silicone dioxide, magnesium stearate, and for the coating: purified water, hypromellose and polyethyleneglycole. Candurin® pigments are included for color modification.				
Route of Administration	Oral					
Dosing instructions:	Once daily along with first levodopa dose of the day					
Packaging and Labeling	Study Intervention will be provided in PVC/PVDC60/Al blisters. Sufficient blisters of 10 tablets will be paced in cases, sufficient for each visit interval. Each case with blisters will be labeled as required per country requirement.					
Manufacturer	Catalent, Schorndorf, Germany in alternative Zambon Spa, Vicenza, Italy	Zambon Spa, Vicenza, Italy				

Primary packaging	Zambon Spa,	Zambon Spa,
	Vicenza, Italy	Vicenza, Italy
	in alternative	in alternative
	Catalent, Schorndorf,	Catalent, Schorndorf,
	Germany	Germany
Secondary packaging & labeling	Almac, Craigavon, United Kingdom	Almac, Craigavon, United Kingdom

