6.4. Study Intervention Compliance

Compliance will be assessed based on drug accountability.

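### SAP 3.3.7 counts every unreturned tablet as taken, so missed doses can never put a participant who returns no packs below 80% compliance

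*SAP*

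**What the plan says.** Protocol 6.4 gives one basis for adherence: "Compliance will be assessed based on drug accountability". SAP 3.3.7 turns that into a percentage, "100 x (# of tablets dispensed - # of tables returned) / # of tablets expected to be taken", and then states: "If study drug is not returned, the number of tablets returned and lost will be considered 0 for the compliance calculation". The formula contains no term for lost tablets, although the rule mentions them. Versions 1.0 and 2.0 of the SAP carry the same text.

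The expected count runs from randomisation to Visit 6 for participants who complete that visit. It stops at the last visit "if subjects early terminated prior to Week 12 / Visit 6". A further line says: "Any drug interruptions or temporary discontinuation will be taken into account". It does not say how. Results are summarised by treatment with descriptive statistics and in three bands: below 80%, 80-120% and above 120%. The SAP does not label any band as compliant.

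The tablet count handed out at each visit is not given. Protocol 6.1 says only: "Sufficient blisters of 10 tablets will be paced in cases, sufficient for each visit interval".

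**The concern.** An unreturned pack carries no information about intake. Setting its returned count to 0 replaces that gap with the most favourable value: every tablet swallowed. This is a stated rule that yields a wrong number, not an omitted detail, and it acts on the participants whose intake is least known.

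The primary objective is the safety and tolerability of safinamide 200 mg once daily, so a reader of the report will want to know how much drug was taken. No other planned measure would expose the error. Pharmacokinetics are not evaluated (Protocol 8.5), and days of exposure in SAP 3.3.7 run from first to last dose without allowing for interruptions. Incomplete returns are plausible. Under the COVID-19 measures, drug could be shipped home (Protocol 6.2) and Visits 3 to 6 could be held remotely (Protocol 1.3 and Section 8). With about 32 and 16 participants per arm (48 randomised 2:1), a few wrong scores would be visible in the table.

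**Working it through.** The documents state no compliance figure, so there is none to reproduce. The SAP 3.3.7 formula is applied directly.

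**Inputs**
- Visit days 1, 14, 28, 56 and 84, with a window of ±3 days after baseline (Protocol 1.3).
- One tablet a day for two weeks, then two a day (Protocol 1.1).
- Blisters of 10 (Protocol 6.1). The number dispensed per visit is an assumption and is varied below.

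**Expected tablets, on-schedule completer**

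(84 − 14 + 1) × 2 + (14 − 1) = 142 + 13 = 155.

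**Completer who returns nothing:** score = 100 × dispensed / 155

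| Assumed supply over the four intervals | Dispensed | Score | Band |
|---|---|---|---|
| Exact nominal need, 14 + 28 + 56 + 56 | 154 | 99.4% | 80-120% |
| Whole blisters, 20 + 30 + 60 + 60 | 170 | 109.7% | 80-120% |
| Exact need plus 3 days each, 17 + 34 + 62 + 62 | 175 | 112.9% | 80-120% |
| Whole blisters plus 3 days each, 20 + 40 + 70 + 70 | 200 | 129.0% | above 120% |

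The band changes at 1.2 × 155 = 186 tablets. Moving Visits 3 and 6 within their windows gives 170/164 = 103.7% to 170/146 = 116.4% for 170 tablets, and 122.0% to 137.0% for 200. A score below 80% would need fewer than 0.8 × 155 = 124 tablets dispensed, which is less than the nominal need. Intake appears nowhere in the calculation. A participant who took only the first doses planned at the site at Visits 2 and 3 (1 + 2 = 3 tablets, 3/155 = 1.9%) gets the same score as one who took everything.

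**Early leaver who returns nothing** (20/30/60/60 supply; expected count stops at the last visit)

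| Last visit | Dispensed | Expected | Score |
|---|---|---|---|
| Day 7 | 20 | 7 | 286% |
| Day 19 | 50 | 25 | 200% |
| Day 39 | 110 | 65 | 169% |
| Day 63 | 170 | 113 | 150% |
| Day 75 | 170 | 137 | 124% |

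These leavers fall in 80-120% only with a last visit at about Days 53-55 (Day 53: 110/93 = 118%) or from Day 78 (170/143 = 119%). In an arm of 16, replacing one score of 100% by 200% moves the arm mean by 100/16, about 6 points.

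**Only the last pack unreturned and untaken** (170 dispensed, no interruption recorded)
- Taken to Day 55: 13 + 28 + 56 = 97 tablets.
- Returned from the first three packs: 7 + 2 + 4 = 13 tablets.
- Score: (170 − 13)/155 = 157/155 = 101.3%.
- True compliance: 97/155 = 62.6%.

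If the four weeks without drug are recorded as an interruption, the expected count falls by 2 × (84 − 56 + 1) = 58 to 97. The score becomes 157/97 = 162%. The participant then leaves the middle band, but in the wrong direction.

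**The case against.** The strongest reply is that this is a descriptive variable in a pilot and feeds no model or test. Tolerability is read from adverse events leading to interruption, reduction or discontinuation (SAP 3.5.1) and from withdrawals with reasons (SAP 2.3.2 and 3.3.1). Early leavers who return nothing mostly stand out above 120%, and recorded interruptions push completers the same way: seven days at two tablets gives 170/141 = 120.6%. Hidden under-use therefore requires missed doses that are also unreported. Early leavers are asked to complete the end-of-treatment assessments, which include drug accountability. The measure "to manage study medication return at site through a care-giver/family member" (Protocol Section 8, Visit 6) helps packs come back.

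Most of this stands, and it limits the point in two ways. A reader might infer that anyone who returns nothing scores about 110% and is classed as compliant. The documents do not support that: 110% depends on an assumed supply, the band has no such label, and most early leavers land elsewhere. A reader might also infer that poor takers are hidden from the Per-Protocol review. No compliance threshold appears in Protocol 9.3.4 or SAP 3.2.4, and deviations are defined in a separate plan. The Per-Protocol analysis is limited to UMSARS, and is run only if that population is below 90% of the ITT Population.

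What the reply does not remove is the wrong number. A score above 120% does not safeguard against the error, because it reports over-use where intake is unknown and enters the arm means. The rule also leaves the below-80% band unable to catch missed doses in anyone who returns nothing.

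**Conclusion.** The rule is wrong for participants who do not return packs, and this follows from the SAP text without any assumption about supply beyond its being enough for each interval. The size depends on quantities that the documents do not give. It is 99% to 129% for an on-schedule completer who returns nothing, mostly above 120% for early leavers under the 20/30/60/60 supply, and 101% against 63% in the last-pack example, which also needs the missed doses to be unrecorded. How often packs went unreturned is not stated either.

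The consequence that is shown is an incorrect compliance table, in a trial where drug accountability is the only basis for compliance. An effect on the Per-Protocol set, the efficacy analyses or the tolerability conclusions is possible but not shown.

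**What to change.** In SAP 3.3.7, replace the rule that sets returned and lost tablets to 0 with the following:
- Treat accountability as unknown for any pack that is not returned.
- Summarise compliance for participants with complete accountability.
- Report by arm the number of participants with unreturned packs.
- For those participants, show bounds: all unreturned tablets taken, and none taken. In the last-pack example these are 101.3% and 62.6%.

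The bounds matter because participants who return their packs may be the better takers, so the complete-accountability summary alone could flatter adherence. The cost is a change of SAP wording, minor programming, and a few participants with missing or bounded compliance. Trial conduct and treatment are unaffected.
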